### 6.1.3 Surgical Study Cohort

The Surgical Study Cohort will open, once the Safety Lead-In in the Main Study Cohort is completed. We will use a single-stage design and enroll a total of 16 patients

After all screening, registration and baseline procedures have been completed as detailed on the **Schedule of Events (Appendix 1)**, subjects will begin study treatment as below:

CONFIDENTIAL

This material is the property of the NYU School of Medicine. Do not disclose or use except as authorized in writing by the study sponsor

On C1D-29, all subjects will initiate study treatment with one dose of nivolumab IV (3 mg/kg) followed by one dose of ipilimumab IV (1 mg/kg).

On C1D-15, all subjects in this cohort will undergo craniotomy and tumor re-resection.

On C1D1, all subjects will receive nivolumab IV (3 mg/kg)

On C1D8, all subjects will begin radiotherapy (RT) to a total dose of 45 Gy, given in 15 consecutive fractions of 3 Gy each fraction.

On C1D15, subjects will receive nivolumab 3 mg/kg and ipilimumab 1 mg/kg IV. Thereafter, nivolumab administration will continue once every 2 weeks and ipilimumab administration will continue once every 6 weeks.

## **6.2 Dose Delay and Discontinuation Criteria**

### **6.2.1 Immune-Related Adverse Events (irAEs)**

Special attention must be paid to adverse events (AEs) that may be suggestive of a potential immune-mediated pathophysiology. Since inhibition of immune checkpoints stimulates the immune system, immune-mediated adverse events may occur.

Immune-related adverse events (irAEs) are AEs of immune nature (i.e., inflammatory) in the absence of a clear alternative etiology. Immune-mediated AEs are specific events (that include pneumonitis, diarrhea/colitis, hepatitis, nephritis/renal dysfunction, rash, and endocrine [adrenal insufficiency, hypothyroidism/thyroiditis, hyperthyroidism, diabetes mellitus, and hypophysitis]) for which subjects received immunosuppressive medication for treatment of the event, with the exception of endocrine events (hypothyroidism/thyroiditis, hyperthyroidism, hypophysitis, diabetes mellitus, adrenal insufficiency), which are included regardless of treatment since these events are often managed without immunosuppression.

IrAEs include events, regardless of causality, occurring within 100 days of the last dose. IrAEs are limited to subjects who received immunosuppressive medication for treatment of the event, with the exception of endocrine events (hypothyroidism/thyroiditis, hyperthyroidism, hypophysitis, diabetes mellitus, adrenal insufficiency), which are included regardless of treatment since these events are often managed without immunosuppression.

An irAE can occur shortly after the first dose or several months after the last dose of treatment. All AEs of unknown etiology associated with drug exposure should be evaluated to determine possible immune etiology. If an irAE is suspected, efforts should be made to rule out neoplastic, infectious, metabolic, toxin or other etiologic causes. Subjects who develop a Grade 2 or higher irAE should be discussed immediately with the overall Principal Investigator.

### **Management Algorithms for Immuno-Oncology Agents**

Immuno-oncology (I-O) agents are associated with AEs that can differ in severity and duration than AEs caused by other therapeutic classes. Nivolumab and ipilimumab are considered immuno-oncology agents in this protocol. Early recognition and management of AEs associated with immuno-oncology agents may mitigate severe toxicity. Management Algorithms have been developed to assist investigators in assessing and managing the following groups of AEs (see Appendix 4 and the **nivolumab and ipilimumab Investigator Brochures**):

- Gastrointestinal
- Renal
- Pulmonary

CONFIDENTIAL

This material is the property of the NYU School of Medicine. Do not disclose or use except as authorized in writing by the study sponsor

- Hepatic
- Endocrinopathy
- Skin
- Neurological (non-brain/intracranial edema related)

Notes:

- For specific **rules for managing brain/intracranial edema**, see Section 6.1.3.7 below.
- These recommendations should be seen as guidelines, and the treating physician should exercise clinical judgment based on the symptoms and condition of the individual patient
- Refer to the specific dose delay and discontinuation criteria in the following sections for management of study drug-related AEs.

## 6.2.2 Nivolumab and Ipilimumab Dose Modification

Once the doses of nivolumab and ipilimumab are established in the Safety Lead-In portion of the study, **no dose reductions of nivolumab and ipilimumab will be allowed**. During the Safety Lead-in portion of the study, dose reductions for an individual subject will not be allowed.

## 6.2.3 Nivolumab and Ipilimumab Dose Delay Criteria

If nivolumab and ipilimumab dosing is delayed, the cycle count should be interrupted.

Tumor assessments for all subjects should continue as per protocol even if dosing is delayed.

Subjects who experience an adverse event that requires a treatment delay should be monitored with appropriate laboratory testing or other clinical evaluation at least weekly until resolution.

Safety Lead-In: All subjects who experience protocol-defined **DLTs** (either during or outside the DLT observation period) during the Safety Lead-In will be required to permanently discontinue treatment with nivolumab and ipilimumab. In addition, dose delay and discontinuation guidelines are provided below.

For all subjects: Nivolumab and ipilimumab administration should be delayed for the following:

- Any Grade  $\geq$  2 non-skin, drug-related adverse event, except for fatigue, laboratory abnormalities, and brain/intracranial edema (for **rules for managing brain/intracranial edema**, see Section 6.1.3.7 below)
- Any Grade  $\geq$  3 skin drug-related AE
- If a subject has a baseline AST, ALT, or total bilirubin that is within normal limits, delay dosing for Grade  $\geq$  2 AST, ALT, or total bilirubin level elevation
- If a subject has baseline AST, ALT, or total bilirubin within the Grade 1 toxicity range, delay dosing for Grade  $\geq$  3 AST, ALT, or total bilirubin level elevation
- Any Grade  $\geq$  3 drug-related amylase or lipase abnormality that is not associated with symptoms or clinical manifestations of pancreatitis does not require dose delay.
- Any other Grade  $\geq$  3 drug-related laboratory abnormalities with the exception of Grade 3 lymphopenia which does not require a dose delay.
- Any AE, laboratory abnormality or inter-current illness which, in the judgment of the investigator, warrants delaying the dose of study medication.

Subjects receiving ipilimumab in combination with nivolumab that have drug-related toxicities that meet the criteria for dose delay should have both drugs (ipilimumab and nivolumab) delayed until retreatment criteria are met. Exceptions apply to the retreatment criteria after dose delay of ipilimumab

CONFIDENTIAL

This material is the property of the NYU School of Medicine. Do not disclose or use except as authorized in writing by the study sponsor

and nivolumab for Grade  $\geq 3$  amylase and lipase abnormalities that are not associated with symptoms or clinical manifestations of pancreatitis and that are attributed to ipilimumab alone.

- Nivolumab may be delayed until the next planned ipilimumab dose if the next ipilimumab dose is scheduled within the next 18 days. This will permit periodic ipilimumab dosing to be synchronized with nivolumab dosing.
- Ipilimumab should be dosed at the specified interval regardless of any delays in intervening nivolumab doses. However, in order to maintain periodic synchronized dosing of ipilimumab and nivolumab, the dosing days of nivolumab and ipilimumab may be adjusted within the permitted  $\pm 5$  day window, as long as consecutive nivolumab doses are given at least 16 days apart. Ipilimumab may be delayed beyond the 5 day window if needed to synchronize with the next nivolumab dose.
- If an ipilimumab dose is delayed beyond 6 weeks from the prior ipilimumab dose, then subsequent ipilimumab doses should rescheduled to maintain the 6-week interval between consecutive ipilimumab doses.
- A dose delay of ipilimumab which results in no ipilimumab dosing for  $> 12$  weeks requires ipilimumab discontinuation, with exceptions as noted in Section 6.2.4.2.

#### 6.2.3.1 Criteria to Resume Nivolumab Dosing

Subjects may resume treatment with nivolumab when the drug-related AE(s) resolve(s) to Grade  $\leq 1$  or baseline, with the following exceptions:

- Subjects may resume treatment in the presence of Grade 2 fatigue.
- Subjects with Grade 2 skin toxicity can be treated if no prior experience of Grade  $\geq 3$  drug-related skin AE.
- Subjects with combined Grade 2 AST/ALT AND total bilirubin values meeting discontinuation parameters (Section 6.1.3.5) should have treatment permanently discontinued.
- For subjects with Grade 2 AST, ALT, OR total bilirubin elevations, dosing may resume when laboratory values return to baseline and management with corticosteroids, if needed, is complete.
- Drug-related pulmonary toxicity, diarrhea, or colitis must have resolved to baseline before treatment is resumed. Subjects with persistent Grade 1 pneumonitis after completion of a steroid taper over at least 1 month may be eligible for retreatment if discussed with and approved by the Sponsor.
- Subjects who received systemic corticosteroids for management of any drug-related toxicity must be off corticosteroids or have tapered down to an equivalent dose of prednisone  $\leq 10$  mg/day.
- Drug-related endocrinopathies adequately controlled with only physiologic hormone replacement may resume treatment after consultation with the Sponsor.
- Subjects who delay study treatment due to any Grade  $\geq 3$  amylase or lipase abnormality that is not associated with symptoms or clinical manifestations of pancreatitis, and that is assessed by the investigator to be related to ipilimumab and not to nivolumab, may resume nivolumab when the amylase or lipase abnormality has resolved to Grade  $< 3$ . The Sponsor should be consulted prior to resuming nivolumab in such subjects
- Subjects with Grade  $\leq 3$  treatment-related brain/intracranial edema may resume nivolumab if the grade 3 AE downgrades to Grade  $\leq 1$  within 7 days after onset (for **rules for managing brain/intracranial edema**, see Section 6.2.5)

CONFIDENTIAL

This material is the property of the NYU School of Medicine. Do not disclose or use except as authorized in writing by the study sponsor

#### 6.2.3.2 Criteria to Resume Ipilimumab Dosing

Subjects may resume treatment with ipilimumab when drug-related AE(s) resolve(s) to Grade 1 or baseline value, with the following exceptions:

- Subjects may resume treatment in the presence of Grade 2 fatigue.
- Subjects who have not experienced a Grade 3 drug-related skin AE may resume treatment in the presence of Grade 2 skin toxicity.
- Subjects with baseline Grade 1 AST/ALT or total bilirubin who require dose delays for reasons other than a 2-grade shift in AST/ALT or total bilirubin may resume treatment in the presence of Grade 2 AST/ALT or total bilirubin.
- Subjects with combined Grade 2 AST/ALT and total bilirubin values meeting discontinuation parameters (Section 6.1.3.5) should have treatment permanently discontinued.
- Drug-related pulmonary toxicity, diarrhea, or colitis must have resolved to baseline before treatment is resumed.
- Subjects who received systemic corticosteroids for management of any drug-related toxicity must be off corticosteroids or have tapered down to an equivalent dose of prednisone  $\leq$  10 mg/day.
- Drug-related endocrinopathies adequately controlled with only physiologic hormone replacement may resume treatment after consultation with the Sponsor.
- Dose delay of ipilimumab which results in no ipilimumab dosing for  $>$  12 weeks requires ipilimumab discontinuation, with exceptions as noted in Section 6.2.4.2.
- Ipilimumab may not be resumed sooner than 6 weeks ( $\pm$  5 days) after the prior ipilimumab dose.
- Subjects with Grade  $\leq$  3 treatment-related brain/intracranial edema may resume ipilimumab if the grade 3 AE downgrades to Grade  $\leq$  2 within 7 days, or to Grade  $\leq$  1 or baseline within 14 days after onset (for **rules for managing brain/intracranial edema**, see Section 6.2.5)
- In general, subjects who meet criteria to resume ipilimumab will also have met criteria to resume nivolumab, so it should be feasible to synchronize dosing of both drugs when resuming ipilimumab. In order to facilitate this, the dosing days of nivolumab and ipilimumab may be adjusted within the permitted  $\pm$  5 day window, as long as consecutive nivolumab doses are given at least 18 days apart.
- One exception to note is when ipilimumab and nivolumab doses are delayed due to drug-related Grade  $\geq$  3 amylase or lipase abnormalities not associated with symptoms or clinical manifestations of pancreatitis. If the investigator assesses the Grade  $\geq$  3 amylase or lipase abnormality to be related to ipilimumab and not related to nivolumab, nivolumab may be resumed when the amylase or lipase abnormality resolves to Grade  $<$  3 but ipilimumab may only be resumed when the amylase or lipase abnormality resolves to Grade 1 or baseline. Investigator attribution of this toxicity to the ipilimumab dosing must be clearly noted in the subject's medical chart. The Sponsor should be consulted prior to resuming nivolumab in such subjects.

#### 6.2.4 Treatment Discontinuation Criteria

For all subjects, global deterioration of health status requiring discontinuation of treatment without objective evidence of disease progression at that time should be reported as 'symptomatic deterioration' in the source data and in the case report form. Every effort should be made to document objective progression (i.e., radiographic confirmation) even after discontinuation of treatment.

The assessment for discontinuation of ipilimumab should be made separately from the assessment made for discontinuation of nivolumab. Although there is overlap among the discontinuation criteria, if

CONFIDENTIAL

This material is the property of the NYU School of Medicine. Do not disclose or use except as authorized in writing by the study sponsor

discontinuation criteria are met for ipilimumab but not for nivolumab, treatment with nivolumab may continue if ipilimumab is discontinued.

If a subject meets criterion for permanent discontinuation and investigator is unable to determine whether the event is related to both or one study drug, the subject should discontinue both nivolumab and ipilimumab and be taken off the treatment phase of the study.

Note: Infusion-related reactions, hypersensitivity reactions (Grades 1 to 4), should be handled according to Section 6.2.8.

Note: See Section 8.1, Adverse Event Definitions, for expected AEs related to nivolumab and ipilimumab. Brain edema is an expected AE related to RT.

Decision to discontinue is determined at the time that the treatment discontinuation criteria is met. End of treatment procedures should follow as outlined in 6.7.

#### 6.2.4.1 Nivolumab Dose Discontinuation

Treatment with nivolumab should be permanently discontinued for any of the following:

- Any Grade 2 drug-related uveitis or eye pain or blurred vision that does not respond to topical therapy and does not improve to Grade 1 severity within the treatment re-initiation period OR requires systemic treatment
- Any Grade  $\geq$  2 drug-related pneumonitis or interstitial lung disease that does not resolve to dose delay and systemic steroids (also see Pulmonary Adverse Event Management Algorithm)
- Any Grade 3 drug-related uveitis, pneumonitis, bronchospasm, diarrhea, colitis, neurologic toxicity (other than intracranial/brain edema), hypersensitivity reaction, or infusion reaction, regardless of duration
- Any Grade 3 non-skin, drug-related adverse event lasting  $> 7$  days, with the following exceptions:
  - Grade 3 drug-related endocrinopathies adequately controlled with only physiologic hormone replacement do not require discontinuation.
  - Grade 3 symptoms attributable to brain/intracranial edema that downgrades to Grade  $\leq 2$  within 7 days, or to Grade  $\leq 1$  or baseline within 14 days do not require discontinuation (for **rules for managing brain/intracranial edema**, see Section 6.2.5)
- Grade 3 drug-related laboratory abnormalities do not require treatment discontinuation except:
  - Grade 3 drug-related thrombocytopenia  $> 7$  days or associated with bleeding requires discontinuation.
  - Any drug-related liver function test (LFT) abnormality that meets the following criteria require discontinuation (also see Hepatic Adverse Event Management Algorithm):
    - AST or ALT  $> 5 \times$  ULN for  $> 4$  weeks
    - Any AST or ALT measurements  $> 20 \times$  ULN
    - Any Total bilirubin  $> 3 \times$  ULN
    - Concurrent AST or ALT ( $> 3 \times$  ULN) and total bilirubin ( $> 1.5 \times$  ULN)
- Any Grade 4 drug-related adverse event or laboratory abnormality, except for the following events, which do not require discontinuation:
  - Grade 4 neutropenia  $\leq 7$  days

CONFIDENTIAL

This material is the property of the NYU School of Medicine. Do not disclose or use except as authorized in writing by the study sponsor

- Grade 4 lymphopenia or leukopenia
- Isolated Grade 4 amylase or lipase abnormalities that are not associated with symptoms or clinical manifestations of pancreatitis and decrease to < Grade 4 within 1 week of onset. The Sponsor should be consulted for Grade 4 amylase or lipase abnormalities
- Isolated Grade 4 electrolyte imbalances/abnormalities that are not associated with clinical sequelae and are corrected with supplementation/appropriate management within 72 hours of their onset.
- Grade 4 drug-related endocrinopathy adverse events such as adrenal insufficiency, ACTH deficiency, hyper- or hypothyroidism, or glucose intolerance, which resolve or are adequately controlled with physiologic hormone replacement (corticosteroids, thyroid hormones) or glucose controlling agents, respectively, may not require discontinuation after discussion with and approval from the Sponsor.
- Dosing delay of nivolumab which results in treatment interruption of > 6 weeks requires treatment discontinuation with the following exceptions:
  - Dosing delays to allow for prolonged steroid tapers to manage drug-related adverse events are allowed. Prior to re-initiating treatment in a subject with a dosing delay lasting > 6 weeks from the previous dose, the Sponsor must be consulted. Tumor assessments should continue as per protocol even if dosing is delayed. Periodic study visits to assess safety and laboratory studies should also continue every 6 weeks or more frequently if clinically indicated during such dosing delays.
  - Dosing delays lasting > 6 weeks from the previous dose that occur for non-drug-related reasons may be allowed if approved by the Sponsor. Prior to re-initiating treatment in a subject with a dosing delay lasting > 6 weeks, the Sponsor must be consulted. Tumor assessments should continue as per protocol even if dosing is delayed.
  - Periodic study visits to assess safety and laboratory studies should also continue every 6 weeks or more frequently if clinically indicated during such dosing delays.
- Any adverse event, laboratory abnormality, or intercurrent illness which, in the judgment of the Investigator, presents a substantial clinical risk to the subject with continued nivolumab dosing.

#### 6.2.4.2 Ipilimumab Dose Discontinuation

Ipilimumab should be permanently discontinued if any of the following criteria are met:

- Any Grade  $\geq$  2 drug-related uveitis or eye pain or blurred vision that does not respond to topical therapy and does not improve to Grade 1 severity within 2 weeks OR requires systemic treatment;
- Any Grade  $\geq$  3 bronchospasm or other hypersensitivity reaction
- Any other Grade 3 non-skin, drug-related adverse event with the following exceptions:
  - Grade 3 nausea and vomiting
  - Grade 3 neutropenia and thrombocytopenia
  - Symptomatic endocrinopathies which resolved (with or without hormone substitution)
  - Grade  $\leq$  3 symptoms attributable to brain/intracranial edema that downgrades to Grade  $\leq$  2 within 7 days, or to Grade  $\leq$  1 or baseline within 14 days after onset (for **rules for managing brain/intracranial edema**, see Section 6.2.5)
- Any drug-related liver function test (LFT) abnormality that meets the following criteria require discontinuation:
  - AST or ALT  $>$  5 x ULN for > 2 weeks

CONFIDENTIAL

This material is the property of the NYU School of Medicine. Do not disclose or use except as authorized in writing by the study sponsor

- Any AST or ALT measurements  $> 20 \times \text{ULN}$
  - Any Total bilirubin  $> 3 \times \text{ULN}$
  - Concurrent AST or ALT ( $> 3 \times \text{ULN}$ ) and total bilirubin ( $> 1.5 \times \text{ULN}$ )
- Any Grade 4 drug-related adverse event or laboratory abnormality, except for the following events, which do not require discontinuation:
  - Grade 4 neutropenia  $\leq 7$  days
  - Grade 4 lymphopenia or leukopenia
  - Isolated Grade 4 amylase or lipase abnormalities which are not associated with symptoms or clinical manifestations of pancreatitis. The Sponsor should be consulted for Grade 4 amylase or lipase abnormalities
  - Isolated Grade 4 electrolyte imbalances/abnormalities that are not associated with clinical sequelae and are corrected with supplementation/appropriate management within 72 hours of their onset
  - Grade 4 drug-related endocrinopathy adverse events such as adrenal insufficiency, ACTH deficiency, hyper- or hypothyroidism, or glucose intolerance, which resolve or are adequately controlled with physiologic hormone replacement (corticosteroids, thyroid hormones) or glucose controlling agents, respectively, may not require discontinuation after discussion with and approval from the Sponsor.
- Any treatment delay resulting in no ipilimumab dosing for  $> 12$  weeks with the following exceptions:
  - Dosing delays to manage drug-related adverse events, such as prolonged steroid tapers, are allowed. Prior to re-initiating treatment in a subject with a dosing delay lasting  $> 12$  weeks, the Sponsor must be consulted. Tumor assessments should continue as per protocol even if dosing is delayed.
  - Dosing delays lasting  $> 12$  weeks from the previous dose that occur for non-drug related reasons may be allowed if approved by the Sponsor. Prior to re-initiating treatment in a subject with a dosing delay lasting  $> 12$  weeks, the Sponsor must be consulted. Tumor assessments should continue as per protocol even if dosing is delayed.
- Any adverse event, laboratory abnormality, or intercurrent illness which, in the judgment of the Investigator, presents a substantial clinical risk to the subject with continued nivolumab dosing

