  - AST or ALT ( $> 5 \times \text{ULN}$ ) for  $> 2$  weeks
  - AST or ALT ( $> 8 \times \text{ULN}$ )
  - Total bilirubin ( $> 5 \times \text{ULN}$ )
  - Concurrent AST or ALT ( $> 3 \times \text{ULN}$ ) and total bilirubin ( $> 2 \times \text{ULN}$ )
- Grade  $\geq 3$  lymphopenia will not be classified as DLT as this is frequently observed at baseline in newly diagnosed GBM patients.

CONFIDENTIAL

This material is the property of the NYU School of Medicine. Do not disclose or use except as authorized in writing by the study sponsor

- Isolated grade  $\geq 3$  electrolyte abnormalities that are asymptomatic, considered unrelated or unlikely related to study treatment, and are reversed within 48 hours with replacement will not be considered DLT. However, recurrence of the same grade  $\geq 3$  electrolyte abnormality during the DLT period will be considered a DLT.

While rules for adjudicating DLTs are specified above, an AE of Grade  $<3$  (except if listed as exempt above), may also be defined as a DLT after a consultation with the overall study Principal Investigator, based on the safety profile of nivolumab and/or ipilimumab. In the absence of clinical abnormality, repeat laboratory testing will be conducted to confirm significant laboratory findings prior to designation as a DLT.

For guidance on assessing the relationship of AEs to nivolumab and ipilimumab, RT, or study procedures, see Appendix 5. The sponsor may request information to justify the causality assessment of DLTs, as needed.

**Note:** See Section 8.1, Adverse Event Definitions, for **expected AEs** related to nivolumab or ipilimumab.

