#### **Abnormal Laboratory Values**

All laboratory test results captured as part of the study should be recorded following institutional procedures.

A clinical laboratory abnormality should be documented as an adverse event if any one of the following conditions is met:

- The laboratory abnormality is not otherwise refuted by a repeat test to confirm the abnormality
- The abnormality suggests a disease and/or organ toxicity
- The abnormality is of a degree that requires active management; e.g. more frequent follow-up assessments, further diagnostic investigation, specific corrective therapy, etc.
- The abnormality leads to a change in dosing (outside of protocol-stipulated dose adjustments)
- The abnormality leads to discontinuation from the study, significant additional concomitant medication, or other therapy
- The laboratory test result is clinically significant or meets the definition of an SAE

CONFIDENTIAL

This material is the property of the NYU School of Medicine. Do not disclose or use except as authorized in writing by the study sponsor

Contact the sponsor in the event the investigator feels that an abnormal test finding should be reported as an AE, although it does not meet any of the above criteria.

Test results that constitute SAEs should be documented and reported as such per the guidelines outlined in Section 8.4.

Repeating an abnormal test, in the absence of any of the above conditions, does not constitute an AE. Any abnormal test result that is determined to be an error does not require reporting as an AE.

Evaluation of severity of laboratory abnormalities will be assessed according to the scale outlined in Section 8.2.1.

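### Read literally, Section 6.2.4.2 permanently stops ipilimumab for four kinds of drug-related Grade 3 laboratory event that it exempts at Grade 4

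*Combined protocol and SAP*

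**What the plan says.** Section 6.2.4.2 sets the permanent stopping criteria for ipilimumab. One criterion is "Any other Grade 3 non-skin, drug-related adverse event with the following exceptions". It has no duration limit. Its exceptions are nausea and vomiting, neutropenia and thrombocytopenia, endocrinopathies that resolved, and brain-edema symptoms that downgrade in time. A separate criterion covers liver function tests. A further criterion covers Grade 4 events and has its own exceptions, among them "Grade 4 lymphopenia or leukopenia", isolated amylase or lipase elevations without pancreatitis symptoms, and isolated electrolyte disturbances without sequelae that are corrected within 72 hours.

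Other sections bear on the same events:

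- Section 6.2.3, which governs delay of both drugs, requires delay for other Grade 3 or higher "drug-related laboratory abnormalities with the exception of Grade 3 lymphopenia which does not require a dose delay". It adds that a Grade 3 or higher "drug-related amylase or lipase abnormality that is not associated with symptoms or clinical manifestations of pancreatitis does not require dose delay".
- Section 6.2.3.2 gives a general rule, "Subjects may resume treatment with ipilimumab when drug-related AE(s) resolve(s) to Grade 1 or baseline value, with the following exceptions". For amylase and lipase attributed to ipilimumab alone, it says that "ipilimumab may only be resumed when the amylase or lipase abnormality resolves to Grade 1 or baseline".
- Section 6.1.1.1 says that Grade 3 or higher "lymphopenia will not be classified as DLT as this is frequently observed at baseline in newly diagnosed GBM patients".
- Section 6.2.4.1, for nivolumab, exempts Grade 3 drug-related laboratory abnormalities from discontinuation in general. It then names the ones that still require it (certain thrombocytopenia and liver-function results). Section 6.2.4.2 has no such clause.

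**The concern.** A stopping rule should not be stricter for the milder grade of the same event, and the protocol gives no clinical reason for this ordering. The nivolumab section avoids it with one clause, which suggests that the ipilimumab section omits something by oversight.

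What is at stake is a study drug. An investigator who applies 6.2.4.2 as written ends ipilimumab permanently for, say, drug-related Grade 3 lymphopenia. One who relies on 6.2.3 gives the next dose on time. Section 6.2.1 refers investigators to both the delay and the discontinuation criteria and does not rank them, so similar patients could be treated in opposite ways. The investigator who keeps ipilimumab is also, on the literal text, departing from the protocol, and Section 8.4.1 asks for sponsor and IRB approval before a deviation is initiated.

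**Working it through.** No figure in the plan is in question. The check sets the criteria side by side, for drug-related events only.

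**1. Grade 3 against Grade 4 within 6.2.4.2, and specific text elsewhere**

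| Event | Grade 3, literal reading | Grade 4 | Specific conflicting text elsewhere |
|---|---|---|---|
| Lymphopenia | permanent stop | exempt | 6.2.3: no delay at Grade 3 |
| Leukopenia | permanent stop | exempt | none |
| Amylase or lipase, isolated, no symptoms | permanent stop | exempt, sponsor consulted | 6.2.3: no delay; 6.2.3.2: ipilimumab may resume |
| Electrolytes, isolated, no sequelae, corrected within 72 hours | permanent stop | exempt | none |

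**2. Count.** The Grade 4 exceptions are neutropenia of at most 7 days, lymphopenia or leukopenia, amylase or lipase, electrolytes, and endocrinopathy: 5 lines. Neutropenia and endocrinopathy also appear among the Grade 3 exceptions: 2 lines. Unmatched: 5 − 2 = 3 lines. One of these names two events, so 4 event types are inverted.

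**3. Are laboratory findings within the Grade 3 criterion?** Its wording mentions adverse events only, whereas the Grade 4 criterion adds laboratory abnormalities. Two things favor inclusion. First, the Grade 3 criterion exempts neutropenia and thrombocytopenia, which would need no exemption if laboratory findings were outside it. Second, Section 8.1 says "A clinical laboratory abnormality should be documented as an adverse event if any one of the following conditions is met", and one of those conditions is simply that a repeat test has not refuted the result.

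**4. Do the delay rules contradict the stop?** A delay rule and a stopping rule can apply to the same event. Grade 3 colitis meets the delay rule in 6.2.3 for non-skin events of Grade 2 or higher and also the Grade 3 stop in 6.2.4.2, and there is no contradiction in that. A conflict needs text that makes sense only if the drug continues. Such text exists for lymphopenia (no delay needed) and for amylase or lipase (no delay needed, and a stated condition for resuming). For leukopenia and electrolytes there is only the general delay rule and the general resumption rule.

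**5. Reach.** Under 6.2.4 the two drugs are assessed separately, so nivolumab normally continues. Both stop only if the investigator cannot tell which drug is responsible; 6.2.7 has a similar fallback that includes radiotherapy. Under 7.3.2 a patient who has had one dose of study drug stays in the primary analysis. Toxicity monitoring in 3.5.1 counts related Grade 3 events whether or not a drug was stopped.

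**The case against.** The strongest objection concerns scope. Section 6.2.4.2 has its own liver-function criterion, which stops ipilimumab when AST or ALT exceeds 5 times the upper limit of normal for more than 2 weeks. In 6.2.4.1 the corresponding liver limits sit under Grade 3 laboratory abnormalities. If every Grade 3 laboratory value already met the Grade 3 adverse-event criterion, that two-week allowance would have little to do. This stands as evidence of ambiguity. It does not remove the exemption of neutropenia and thrombocytopenia or the breadth of Section 8.1, so inclusion remains the better reading, though not a certain one.

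A second objection is that specific text would ordinarily prevail over a general criterion, so investigators would keep ipilimumab for lymphopenia and for amylase or lipase. Many may well do so. But the protocol states no such precedence, and the argument gives no help with leukopenia or electrolytes.

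A reader might infer that 6.2.3 and 6.2.3.2 contradict the stop for all four event types. They do not: for leukopenia and electrolytes the delay and resumption rules can be read as ordinary layering beneath a stopping rule.

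A reader might also infer a large loss of treatment. With dosing every 6 weeks and 10 months (43.5 weeks) of expected participation under 3.1.3, the whole intervals number 7 (43.5 / 6 = 7.25), so there are 7 + 1 = 8 doses, and a stop after the first loses at most 7. That describes one hypothetical patient and treats participation as treatment time. The documents give no rate for these drug-related Grade 3 events. Lymphopenia in particular may be present at baseline or due to radiotherapy, in which case the criterion is not met unless it worsens on study and is judged drug-related.

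**Conclusion.** The inversion is real on the literal text: 3 of 5 Grade 4 exception lines, covering 4 event types, have no Grade 3 match. A text-specific conflict with other sections exists for 2 of the 4, lymphopenia and asymptomatic amylase or lipase. For the other 2 the problem lies within 6.2.4.2 alone. The conclusion rests on reading the Grade 3 criterion to include laboratory findings, which the text favors without settling, and it applies only to events judged drug-related.

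The consequence is unneeded or inconsistent permanent loss of ipilimumab in an unknown, possibly small, number of patients. The documents do not support a claim of added toxic exposure, since the literal rule removes drug. Nor do they support any effect on the 1-year survival analysis set or on error rates. This looks like a drafting omission that should be corrected, not a flaw in the trial's inference.

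**What to change.** Add to 6.2.4.2 the clause that 6.2.4.1 already has: Grade 3 drug-related laboratory abnormalities do not require discontinuation, except those that meet the existing ipilimumab liver-function criteria. This removes all four inversions and also makes the role of the liver criterion clear.

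The minimum alternative is three further Grade 3 exceptions: lymphopenia or leukopenia; isolated amylase or lipase abnormalities without pancreatitis symptoms; and isolated electrolyte abnormalities without sequelae that are corrected within 72 hours. It is less complete. Other Grade 3 laboratory events, including liver tests below the stated limits, would stay under the same literal stop.

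Delay and resumption remain with 6.2.3 and 6.2.3.2, and the separate stop after a DLT in the Safety Lead-In is untouched. The clinical team should state separately whether asymptomatic amylase or lipase elevation needs no delay, as 6.2.3 says, or a delay until recovery, as 6.2.3.2 presumes.

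The cost is wording in one section: one clause, or three lines. Sample size, analysis and data collection do not change. For the four event types, the minimum alternative tolerates nothing at Grade 3 that the protocol does not already tolerate at Grade 4.
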